#### Sample Size Determination

The sample size for Part 1 is driven by the 3+3+3 trial design and will range from 3 to 9 DLT evaluable patients depending on the number of DLTs which may occur. The main objective for the Part 2 is to perform exploratory biomarker analyses in the LPC setting and to preliminary assess the efficacy in terms of response in the mCRPC setting.

Simon's two-stage design (Simon, 1989) based on the Minimax approach will be used for Part 2 Arm 1A and 1B separately. The null hypothesis that the true response rate is 5% will be tested against a one-sided alternative. In the first stage, 20 evaluable patients will be treated. Enrollment will continue following sponsor decision (upon recommendation from the SRC following review) and 13 additional evaluable patients may be treated for a total of 33 evaluable patients. If there is one or fewer responses in the first 20 evaluable patients, the enrollment for that arm may be stopped. The null hypothesis will be rejected if five or more responses are observed in 33 evaluable patients. This design yields a type I error rate of 2.5% and power of 80% when the true response rate is 20%.

A patient will be considered as evaluable if included in the primary analysis set (mITT set) which is defined as all patients who are randomized to the IMP and

CONFIDENTIAL Page 23 of 122

have a baseline and at least one post-baseline (i.e., one on-treatment or post-treatment) tumor assessment (clinical or imaging assessment).

No formal sample size calculation is performed for the LPC setting in Part 2 (Arms 2 and 3) due to its exploratory nature. However, 20 patients are planned to be enrolled into Arm 2 and Arm 3. Based on this sample size (N=20) the one-sided 95% CI of binary endpoints will have a width of up to +/-0.19 in each group depending on the observed effect size.

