# LPC patients (Part 2 Arms 2 and 3)

Tumor measurement using mpMRI or MRI will be used consistently for assessment. The same imaging modality should be used at screening and at all subsequent assessments. Tumor measurements should be performed at the following time points:

- During the screening period (within 28 days before C1D1 [baseline])
- Prior to surgery (i.e., at the end of C8/EoT visit).

For guidance on the mpMRI, see the Imaging Acquisition Guideline.

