	
- every 8 weeks (± 7 days) for 24 weeks (i.e. between C6D1 and C8D15)- and every 3 months (± 7 days) thereafter, i.e., from C11D15 until disease progression is assessed by the investigator or the start of a new anti-cancer therapy or withdrawal of consent, or death, whichever occurs first- At EoT visit (only if clinically indicated); not required if previous imaging was performed within ≤ 9 weeks before the EoT visit 
Patients in Arm 1B who moved to treatment with cemiplimab monotherapy following progression after W_pro1 monotherapy, should have radiographic assessments performed every 3 months (± 7 days) thereafter, until disease progression is assessed by the investigator or the start of new anti-cancer therapy or withdrawal of consent, or death, whichever occurs first.
 
Part 2 Arms 2 and 3 (LPC):
 
Tumor measurement using multi-parametric MRI (mpMRI) or MRI will be used consistently throughout the trial. The same imaging modality should be used at screening and at all subsequent assessments. Tumor measurements should be performed at the following time points:
 
- during screening period (within 28 days before C1D1)- prior to surgery (i.e. at the end of C8/EoT visit)
--	---

Treatment overview:	
----------------------------	--

Treatment sequence: (if applicable) NIMP ADT is to be administered first, thereafter W_pro1, and then cemiplimab.

Part 1 Dose Titration[&]

Day	C1			C2			C3 →			
	1	8	15	1	8	15	1	8	15	
W_pro1 [§]										
CC1 µg IV	X									
CC1 µg IV		X								
CC1 µg IV			X							
Highest tolerable dose*				X	X	X	X	→ Q3W		

Part 2

Arm 1a (W_pro1 + cemiplimab in mCRPC)

Arm 2[#] (W_pro1 + cemiplimab in LPC)

Day	C1			C2			C3 →			
	1	8	15	1	8	15	1	8	15	
W_pro1 [§]										
CC1 µg IV	X									
CC1 µg IV		X								
CC1 µg IV			X	X	X	X	X	→ Q3W		
Cemiplimab										
CC1 mg IV Q3W	X			X			X	→ Q3W		

Part 2

Arm 1b[%] (W_pro1 monotherapy in mCRPC)

Arm 3[#] (W_pro1 monotherapy in LPC)

Day	C1			C2			C3 →			
	1	8	15	1	8	15	1	8	15	
W_pro1 [§]										
CC1 µg IV	X									
CC1 µg IV		X								
CC1 µg IV			X	X	X	X	X	→ Q3W		

Abbreviations and Footnotes:

LPC = localized prostate cancer; mCRPC = metastatic castration resistant prostate cancer; Q3W = every three weeks.

& Recommended dose range (REDR) is confirmed in Part 1.

* Maximum administered dose CC1 µg; minimum administered dose CC1 µg; no dose re-escalation allowed.

In combination with ADT (e.g., Goserelin).

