6 SAMPLE SIZE DETERMINATION

The sample size for Part 1 is driven by the 3+3+3 trial design and will range from 3 to 9 DLT evaluable patients depending on the number of DLTs which may occur. The main objective for the Part 2 is to perform exploratory biomarker analyses in the LPC setting and to preliminarily assess the efficacy in terms of response in the mCRPC setting.

Simon's two-stage design [5] based on the Minimax approach will be used for Part 2 Arm 1A and 1B separately. The null hypothesis that the true response rate is 5% will be tested against a one-sided alternative. In the first stage, 20 evaluable patients will be treated. Enrollment will continue following the sponsor's decision (upon recommendation from the SRC's review) and 13 evaluable patients may be treated for a total of 33 evaluable patients. If there are 1 or fewer responses in the first 20 evaluable patients, the enrollment for that arm may be stopped. The null hypothesis will be rejected if 5 or more responses are observed in 33 evaluable patients. This design yields a type I error rate of 2.5% and power of 80% when the true response rate is 20%.

A patient will be considered as evaluable if included in the primary analysis set (mITT set, see Section 7.1) which is defined as all patients who are randomized to the IMP and have a baseline and at least one post-baseline (i.e., one on-treatment or post-treatment) tumor assessment (clinical or imaging assessment).

No formal sample size calculation is performed for the LPC setting in Part 2 (Arms 2 and 3) due to its exploratory nature. However, 20 patients are planned to be enrolled into Arm 2 and Arm 3. Based on this sample size (N=20) the one-sided 95% CI of binary

endpoints will have a width of up to +/-0.19 in each group depending on the observed effect size.

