censored and under risk will be displayed for selected time points (e.g. after 3 months, after 6 months and after 12 months).

The survival distributions for two treatment groups will be compared using the log-rank test, and the p-value will be provided. The associated hazard ratio (HR) and two-sided 95% confidence interval will be estimated by using Cox proportional hazard model with treatment as model covariate.

All treatment comparisons, except the analysis defined for the primary efficacy endpoint see Section 4, are purely exploratory. Exploratory treatment comparisons will be performed separately for patients with mCRPC (comparison of Arm 1A versus Arm 1B) and for patients with LPC (comparison of Arm 2 versus Arm 3).

The time-to-event analysis will be illustrated using Kaplan-Meier plots by treatment groups.

Efficacy data collected for patients in Arm 1B after the switch from W_pro1 monotherapy to cemiplimab monotherapy will not be considered in the efficacy analyses. These measurements will only be considered in the exploratory efficacy analyses comprising ORR, DoR, PFS (per PCWG3 and iRECIST (central reading)) and PFS2 on cemiplimab monotherapy based on last tumor assessment prior to start of cemiplimab treatment. These exploratory endpoints to analyze the preliminary anti-tumor activity of cemiplimab monotherapy will be generated using the subsequent cemiplimab monotherapy on progression set. More details regarding these analyses can be found in Section 8.7.4.2.

The safety and tolerability profile of cemiplimab monotherapy will be analyzed using the subsequent cemiplimab monotherapy on progression set. The definition of cemiplimab TEAEs will be provide in detail in Section 8.9.3. All other safety data (e.g. laboratory, electrocardiogram (ECG), vital signs) reported for patients in Arm 1B after the switch to cemiplimab monotherapy will be included in the respective listings.

All relevant data will be listed. The listing will be sorted by treatment group, patient number and date/time of assessment (if applicable). Unscheduled measurements will be included in the listings.

See Section 11 for the definition of planned summary tables, figures and listings. Templates for each unique table and patient listing are provided in a separate document “Mock Tables, Listings and Figures”.

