The number and percentage of patients per PSADT under-treatment on C4D1 and D1 of every fourth subsequent cycle (e.g., C8D1, C12D1, etc.) in Part 1 and Part 2 Arm 1A and 1B, or on C4D1, C8D1, and EoT in Part 2 Arms 2 and 3 compared with baseline. For more details for the calculation of PSADT, see Section 8.2.

The following categorization of PSADT should be reported: 0 - 3 months, >3 – 6 months, >6 – 9 months, >9 – 12 months, >12 – 18 months, >18 – 24 months, >24 months.

Sensitivity analyses will be performed using the ITT set and the PP set depending on the number of patients excluded.

Objective Response Rate for Part 1

For Part 1, ORR is defined as secondary efficacy endpoint as best objective response per PCWG3 and will be analyzed descriptively for the mITT set. For more details, see Section 8.7.1.1.

Tumor assessment post-treatment compared to baseline for Part 2, Arm 2 and Arm 3

Tumor measurements using mpMRI or, if tumor measurement is not feasible with a mpMRI, imaging according to local practice (e.g. CT or MRI), should be performed at the following time points:

- During the screening period (within 28 days before C1D1 (baseline))
- Prior to surgery (i.e. at the end of C8/EoT Visit)

Tumor response will be assessed based on Radiological Soft Tissue Evaluation at both time points. Number of patients in each category and ORR will be summarized with absolute and relative frequencies along with two-sided 95% Clopper-Person CIs by treatment group for the mITT set.

Tumor response assessment including overall response, best overall response and clinical progression as documented in the eCRF will be listed. In addition, listings including all tumor assessments per PCWG3 (target lesion, non-target lesion, new lesion) will be generated.

Sensitivity analyses will be performed using the ITT set and the PP set depending on the number of patients excluded.

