11.1.2 Listings

Header	Listing Number	Name	Analysis Set	Interim Analysis
16.2		Patient Data Listings		
16.2.1		Patient Disposition		
	16.2.1.1	Patient disposition	Screened set	Yes
	16.2.1.2	Informed consent	Screened set	
	16.2.1.3	Patients impacted by COVID-19 related study disruption	ITT set	
	16.2.1.4	Missing visits due to COVID-19	ITT set	
16.2.2		Protocol Deviations		
	16.2.2.1	Protocol Deviations	ITT set	
	16.2.2.2	Protocol Deviation due to COVID-19	ITT set	
16.2.3		Patients Excluded from the Efficacy Analysis		
	16.2.3.1	Inclusion/exclusion criteria not met	Screened set	
	16.2.3.2	Exclusion from analysis set	Screened set	Yes
16.2.4		Demographic Data		
	16.2.4.1	Demographics	ITT set	Yes
	16.2.4.2	Disease characteristics	ITT set	Yes
	16.2.4.3	Medical History	ITT set	
	16.2.4.4	Prior systemic cancer therapies	ITT set	Yes
	16.2.4.5	Prior cancer radiotherapies	ITT set	
	16.2.4.6	Prior cancer surgeries	ITT set	
	16.2.4.7	Prior and concomitant medications	ITT set	
	16.2.4.8	Further antineoplastic therapies	ITT set	
	16.2.4.9	Cancer radiotherapies	ITT set	
	16.2.4.10	Procedures and non-drug therapies	ITT set	
16.2.5		Compliance and/or Drug Concentration Data (if available) (Note; exposure information will be included in this section)		
	16.2.5.1	Trial treatment – W_pro1	Safety set	
	16.2.5.2	Trial treatment – Cemiplimab	Safety set	
	16.2.5.3	Trial treatment – ADT	Safety set	
	16.2.5.4	Drug exposure	Safety set	Yes
16.2.6		Individual Efficacy Response Data		
		Primary and Secondary Efficacy Endpoint		
	16.2.6.1.1	Overall PCWG3 and LPC tumor response assessment based on Radiological Soft Tissue Evaluation per Investigator	ITT set	Yes
	16.2.6.1.2	PCWG3 and LPC tumor assessment based on Radiological Soft Tissue Evaluation per Investigator – target lesions	ITT set	Yes
	16.2.6.1.3	PCWG3 and LPC tumor assessment based on Radiological Soft Tissue Evaluation per Investigator – non-target lesions	ITT set	Yes

Header	Listing Number	Name	Analysis Set	Interim Analysis
	16.2.6.1.4	PCWG3 and LPC tumor assessment based on Radiological Soft Tissue Evaluation per Investigator – new lesions	ITT set	Yes
	16.2.6.1.5	PCWG3 Bone lesions based on Radiological Soft Tissue Evaluation per Investigator – new lesions	ITT set	Yes
	16.2.6.1.6	Clinical progression	ITT set	Yes
	16.2.6.1.7	Overall tumor response assessment based on PCWG3	ITT set	
	16.2.6.2	Prostate-specific antigen (PSA)	ITT set	Yes
		Exploratory Efficacy Endpoints		

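### LPC tumor response is summarized only as response categories and ORR although lesion sizes are collected, and SAP 8.7.3.1 admits CT against the MRI-only rule

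*SAP*

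**What the plan says.** Protocol section 3 makes post-treatment tumor response compared with baseline a secondary endpoint for LPC, without naming a metric. Protocol 9.4.3 adds only that the mITT set is used.

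SAP 8.7.3.1 supplies the method: "Number of patients in each category and ORR will be summarized with absolute and relative frequencies along with two-sided 95% Clopper-Person CIs", by treatment group. Tables 14.2.2.7.1 to 14.2.2.7.3 carry this for the mITT, ITT and PP sets, the last two optional. The sum of target-lesion diameters is among the screening variables in SAP 8.6.2, and individual lesions appear in the listings headed "PCWG3 and LPC tumor assessment based on Radiological Soft Tissue Evaluation per Investigator". For PSA, SAP 8.7.3.1 plans percentage change by visit, categories and waterfall plots.

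On imaging, protocol 8.1.1.1 says for LPC: "Tumor measurement using mpMRI or MRI will be used consistently for assessment". Exclusion criterion 16 removes patients expected to be unable to have mpMRI or MRI. SAP 3.2 repeats the mpMRI/MRI rule and adds: "The same imaging modality should be used at screening and at all subsequent assessments". Footnote 8 of the SAP's LPC schedule says the same. SAP 8.7.3.1, however, asks for mpMRI or, "if tumor measurement is not feasible with a mpMRI, imaging according to local practice (e.g. CT or MRI".

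On size and comparisons, SAP section 6 states that "20 patients are planned to be enrolled into Arm 2 and Arm 3", with no formal calculation. SAP 8.1 foresees exploratory comparisons, among them "for patients with LPC (comparison of Arm 2 versus Arm 3".

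**The concern.** Two patients can have quite different shrinkage and fall in the same category, and two with nearly equal shrinkage can fall either side of the 30% decrease that defines partial response in protocol Appendix 9. With about 20 patients per arm, discarding that detail costs precision the trial has already paid for. It may matter more here because both LPC arms receive ADT, which protocol 2.1.3.1 says leads to tumor regression in most patients. The arms may then differ mainly in degree of shrinkage, which a single cut describes poorly.

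Separately, the section that governs this analysis accepts a scan type that the protocol and the rest of the SAP do not, and gives no rule for scoring it. If a CT were set against a baseline MRI, part of the apparent change could come from the method rather than the tumor.

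**Working it through.** **Inputs.** Arm size 20 (SAP section 6). Partial response at a 30% decrease; progression at a 20% increase that is also at least 5 mm (protocol Appendix 9; the 5 mm condition is ignored below). The documents give no SD, mean change or expected response rate for LPC tumor size, so normality and the values marked *assumed* are mine.

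**1. The plan's own precision figure.** The sample-size text says the one-sided 95% "CI of binary endpoints will have a width of up to +/-0.19 in each group". At a proportion of 0.5:
- plain normal: 1.645 × √(0.25/20) = 0.184
- with n − 1: 1.645 × √(0.25/19) = 0.189
- with t on 19 df: 1.729 × √(0.25/20) = 0.193

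The 0.19 is reproduced by the second and third. The two-sided Clopper-Pearson interval that SAP 8.7.3.1 actually plans reaches up to 0.243 on its longer side (6/20 or 14/20).

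**2. ORR alone.** For a normal variable cut once so that a proportion p respond, the share of information about a shift in the mean that is kept is φ(z_p)² / [p(1 − p)].

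| Response rate | Kept | Equivalent patients of 20 |
|---|---|---|
| 50% | 0.3989²/0.25 = 0.637 | 12.7 |
| 30% or 70% | 0.3477²/0.21 = 0.576 | 11.5 |
| 20% or 80% | 0.2800²/0.16 = 0.490 | 9.8 |
| 10% or 90% | 0.1755²/0.09 = 0.342 | 6.8 |

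The loss for ORR alone is therefore at least 36%.

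**3. All categories.** With ordered categories bounded by standardized cuts a < b, the share kept is the sum over categories of [φ(a) − φ(b)]² / P(category). I placed cuts at −95% (*assumed* stand-in for complete response), −30% and +20%, with *assumed* mean changes from −10% to −50% and SDs from 15 to 30 points.
- Best case in that grid, mean −10%, SD 30: cuts at −2.833, −0.667 and 1.000; 0.0225 + 0.3897 + 0.0102 + 0.3690 = 0.791 kept, a 21% loss.
- Middle case, mean −30%, SD 15: 0.640 kept, a 36% loss, hardly better than ORR because almost nobody is in the outer categories.
- Worst case, mean −50%, SD 15: 0.338 kept, a 66% loss.

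**4. What the continuous summary would give.** For 20 paired measurements, the two-sided 95% CI for a mean is ± 2.093/√20 = ± 0.47 SD.

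**5. Imaging texts side by side.**

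| Place | Scan allowed | Same modality required? |
|---|---|---|
| Protocol 8.1.1.1 | mpMRI or MRI | Yes |
| SAP 3.2 | mpMRI or MRI | Yes |
| SAP LPC schedule, footnote 8 | mpMRI or MRI | Yes |
| SAP 8.7.3.1 | mpMRI; otherwise local practice, CT included | Not stated |
| SAP 13.1 (changes to planned analyses) | No entry | No entry |

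Admitting CT is thus a contradiction both with the protocol and within the SAP, and it is undeclared.

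**The case against.** The endpoint is called tumor response, and response categories implement it directly. They also cover patients for whom no size change exists: the mITT set admits a patient whose only post-baseline assessment is clinical, and target lesions can be absent. Replacing the categories by size change as the main summary would shrink arms that are already small. This objection stands, so the size summary belongs beside the categories.

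The SAP reports every category as well as ORR, lists individual lesions, and may describe more in a separate mock-table document that is not available here. A reader might infer that the arms lose a third or more of their information outright. The documents do not support that: the 36% minimum applies to ORR alone, and step 3 gives scenarios with a loss near 21%.

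A reader might also infer a badly underpowered comparison. For a 0.91 SD shift, which a t-test detects with 80% power at 20 per arm, comparing 50% with 82% responders has 47% power by Fisher's exact test and 59% by chi-square. But protocol 9.1 and SAP section 4 plan no formal comparison, the exploratory comparison in SAP 8.1 follows text on log-rank and Cox methods, and SAP 8.7.3.1 names no test for this endpoint. Fisher's figure also includes that test's own conservatism. The cost is in description, not in a failed test.

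Finally, a reader might infer that the SAP permits an MRI baseline to be paired with a CT. That follows only if SAP 8.7.3.1 is read alone; SAP 3.2 and the schedule footnote still forbid it. CT at both visits would breach the MRI-only rule without mixing modalities. Off-protocol scans can also be examined as deviations at the data review meeting.

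**Conclusion.** The point holds in a limited form, on two counts.

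First, post-baseline LPC lesion sizes are collected but only categorized or listed; no listed table or figure summarizes their change. If percentage change is roughly normal and treatment acts as a shift, ORR keeps at most 64% of the information, and the full category table loses about 21% to 66% over the assumed range. The exact loss cannot be fixed from the documents.

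Second, the CT wording in SAP 8.7.3.1 conflicts with protocol 8.1.1.1, SAP 3.2 and the SAP schedule footnote, and is not declared in SAP 13.1. How many scans it affects is unknown.

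A reader might infer that all LPC activity rests on this table. It does not: PSA decline and PSA doubling time are also secondary endpoints in Arms 2 and 3, PSA is already summarized as continuous change, and PFS is an exploratory endpoint there. Nor is tumor size wholly unused, since its baseline value is summarized. The gap is the change.

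**What to change.** In SAP 8.7.3.1 and the table list:

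1. Keep the categories and ORR. Beside them, add for each LPC arm the percentage change from baseline in the sum of target-lesion diameters (mean and median with 95% CI) and a waterfall plot. State how many patients have no measurable paired scans. Any Arm 2 minus Arm 3 difference, adjusted for baseline size, should be labeled exploratory.
2. Reconcile the CT and local-practice wording with protocol 8.1.1.1 and SAP 3.2. Base the size-change summary on same-modality pairs and list all other pairs.

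The cost is one table and one figure from data already collected. Patients without paired measurements do not contribute to the size-change summary, which is why the categories stay.

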8.7.4 Exploratory analyses

Exploratory efficacy analyses will be performed using the mITT set.

Exploratory efficacy endpoints comprise ORR (in the mCRPC arms and only per iRECIST), DoR, PFS, and OS. Tumor assessments will be performed using PCWG3 for all patient in Part 1 and Part 2 of the trial. For mCRPC patients enrolled in Part 1 and Part 2, tumor assessment using iRECIST (central reading) will be performed in addition.

For mCRPC patients enrolled in Part 1 and Part 2, ORR, DoR, and PFS will be analyzed separately for PCWG3 and iRECIST (central reading).

ORR, and DoR will be analyzed for Part 1 and Part 2 Arms 1A and 1B only.

Sensitivity analyses for exploratory endpoints will be performed using the ITT set and the PP set depending on the number of patients excluded.

In addition, subgroup analyses for some of the exploratory endpoints (i.e. DoR and PFS) will be performed based on the mITT set. The final decision will be made during the DRM.

Exploratory efficacy analyses will also be performed on patients in Arm 1B who are treated with cemiplimab monotherapy following progression after W_pro1 monotherapy. These exploratory analyses will comprise ORR, DoR, PFS (per PCWG3 and iRECIST (central reading)) on cemiplimab monotherapy based on last tumor assessment prior to start of cemiplimab treatment and OS. PFS2 will be analyzed as well. These exploratory efficacy

analyses will be performed using the subsequent cemiplimab monotherapy on progression set.

Exploratory immunogenicity analyses of W_pro1 antigen-specific T-cells based on ELISPOT and further immune monitoring data are not part of this SAP. Respective data will be provided by a central laboratory.

